9.1. Study design

This will be an observational, retrospective, descriptive, multi-national cohort study of children initiating anticoagulation therapy. The study will be conducted using secondary data derived from multiple data sources including electronic health records and administrative health insurance claims data in four European countries (France, Sweden, Denmark, Spain).

The study cohort will include all children aged under two years and initiating anticoagulant therapy following a VTE diagnosis. The inclusion period will be from the market launch date of rivaroxaban oral suspension in each country until end of 2026, with follow-up until end of 2027. Patients will be followed up from the anticoagulation therapy initiation (index date), until occurrence of bleeding (major bleeding, and CRNM bleeding as co-primary outcomes) or recurrent symptomatic VTE (as secondary outcome) – with time at risk specific to each outcome, discontinuation of all study drugs, death, exit or last available data from the data source, or end of study period, whichever occurs first. Two exposure categories will be defined, one for rivaroxaban and one for SOC, using an as-treated exposure definition. Patients will contribute time to both exposure categories if they switch from SOC to rivaroxaban or vice versa. As long as the anticoagulant treatment period is continuing, patients will be allowed to switch multiple times between SOC and rivaroxaban and contribute time accordingly to both exposure categories.

[figure not shown]
If patients have another initiation of anticoagulant therapy for a VTE diagnosis before the age of two years, and for which they fulfil all inclusion and exclusion criteria (including a 6-month washout period), they will be allowed to enter the study cohort again with a new index date.

22195; XAPAEDUS; v 2.1, 16 NOV 2022;

Page 17 of 59

based on template version 9

An overview of the study design is presented in [Figure 1](#).

DOAC = direct oral anticoagulant; SOC = standard of care; VKA = vitamin K antagonist; VTE = venous thromboembolism

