- ^a. Patients will be followed in two exposure categories, rivaroxaban or SOC (heparins, VKAs, other DOACs). Treatment episode of rivaroxaban oral suspension OR SOC defined by cumulative days of supply from consecutive dispensations, until discontinuation (grace period of 30 days allowed and 30-day carry-over period) or switch to other anticoagulation therapy. During an anticoagulation treatment period, switches from SOC to rivaroxaban and vice versa are allowed.
- ^b. Baseline conditions: demographics, characteristics of the index VTE, co-morbidities, prior treatment.
- ^c. Censoring criteria will be the earliest of: discontinuation of all study drugs (rivaroxaban and SOC), death, disenrollment/de-registering/emigration, last available data, end of the study period.

Adapted from Schneeweiss S et al. Graphical Depiction of Longitudinal Study Designs in Health Care Databases. *Ann Intern Med.* 2019 Mar 19;170(6):398-406.

Figure 1 Study design diagram

The strengths of this study design to answer the research question include:

- Use of population-based secondary health data sources which capture observational data from routine clinical practice. This avoids the possibility to influence prescribing behaviour and reduces the risk of selection bias or recall bias due to the secondary nature of the data. The results will reflect prescribing behaviour and risk of outcomes in real-world clinical practice.
- Selection of secondary health data sources providing large population coverage and/or population size, as well as broad coverage of health care settings from different geographical locations and health care systems. This will help: i) maximizing study size in this rare clinical condition, ii) providing ability to identify and follow-up the study population by capturing relevant diagnoses, drugs, and outcomes, and iii) ensuring representativeness for the general target population.
- Use of a new user design, where the at-risk period begins on the date of first observed record of anticoagulation therapy (index date), instead of the preceding VTE date.
- Contextualization of the use of and outcomes with rivaroxaban oral suspension by available contemporary treatment options.

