 - For all agents, a grace period of 30 days will be used. Thus, a treatment episode will be considered discontinued if a gap >30-day grace period is observed between consecutive prescriptions of the same agent. A 30-day period will be added at the end of the treatment episode of each agent to account for a carry-over effect unless a drug switch is observed.
- **Drug switch:** defined whenever a prescription of another anticoagulant agent is recorded during a treatment episode of the prior anticoagulant agent.
- Treatment episodes for the individual SOC agents that are overlapping or separated by less than the 30-day grace period will be collapsed into a single SOC treatment episode.

- **Anticoagulant treatment period:** defined as a sequence of treatment episodes of rivaroxaban and SOC, i.e., from the initial treatment episode of the first agent at index date and all potential consecutive switch(es) to other agents. An anticoagulation treatment period will be considered discontinued when all study drugs of interest are discontinued.

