9.7.6. Sensitivity analysis

9.7.6.1. Sensitivity analysis on exposure

In case of drug switch, the 30-day carry-over period will not be added at the end of the first treatment episode for the main analysis because patients will then contribute time at risk to the switched drug and can only contribute to one exposure category at any given point of time (see [Section 9.3.1](#)). However, patients may actually be using more than one anticoagulant agent at the same time, e.g., when converting from rivaroxaban to VKA. To account for the potential misclassification on exposure during transition and test the impact of the carry-over period, a sensitivity analysis will be conducted, whereby only the first treatment agent episode will be considered, with time at risk including a 30-day carry-over period at the end.

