- Prescriptions may be issued but not dispensed or dispensed but not used. No information will be available to confirm if the medication is actually taken by patient. When available, dispensing data will be preferred over prescription data to minimize the risk of exposure misclassification.
 - Patients may sometimes be exposed to more than one anticoagulant agent at the same time, e.g., when converting from rivaroxaban to VKA. However, at a given time, patients will contribute time at risk to a single exposure category, either rivaroxaban or SOC. In order to test the robustness of the main exposure assumption, a sensitivity analysis will be conducted, whereby only the first treatment agent episode will be considered, with a 30-day carry-over period added at the end of the time at risk.
- Outcomes
 - The definitions of bleeding outcomes are derived from definitions used in clinical trials and require some adaptation within the limitations that exist of available data captured in secondary data sources.
 - The ability to identify bleeding events and their severity will largely depend on the granularity of ICD-9 and ICD-10 codes (diagnoses and procedures), i.e., their sensitivity and specificity in identifying the events of interest. While this type of outcome has already been assessed among adults in previous studies on most data sources, the severity of bleeding might be difficult to determine accurately. Some of the bleedings among children might be more trivial, and will be evaluated as CRNM bleeding, while major bleeding will focus on the most severe events reported during hospitalization, either based on specific bleeding sites or reported with transfusion or as cause of death. Whenever available, prior knowledge on the algorithm to identify these outcomes will be used. The evaluation of these two co-primary bleeding outcomes (major bleeding and CRNM bleeding) with mutually exclusive definitions will allow to provide results with severity grading, thus facilitating the interpretation of study findings.
 - There is a risk of misclassification of the bleeding outcomes because of the uncertainty whether the bleeding event is the actual reason for the hospitalization. It

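### The rule that merges SOC episodes less than 30 days apart makes no exception for rivaroxaban in between, and so conflicts with the switch and as-treated rules

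*Protocol*

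**What the plan says.** Section 9.3.1 first builds treatment episodes by agent and then forms the SOC category: "Treatment episodes for the individual SOC agents that are overlapping or separated by less than the 30-day grace period will be collapsed", so that they count as one SOC episode. The sentence carries no condition about rivaroxaban. The same section sets the grace rule for each agent, under which "a treatment episode will be considered discontinued if a gap >30-day grace period is observed between consecutive prescriptions of the same agent". It defines a drug switch as "defined whenever a prescription of another anticoagulant agent is recorded during a treatment episode of the prior anticoagulant agent".

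Other places govern the same child:

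- The notes to Figure 1 (section 9.1) let a rivaroxaban or SOC episode run "until discontinuation (grace period of 30 days allowed and 30-day carry-over period) or switch to other anticoagulation therapy".
- Section 9.1, repeated in substance in 9.2.2.1, says "patients will be allowed to switch multiple times between SOC and rivaroxaban and contribute time accordingly to both exposure categories" while the anticoagulant treatment period continues.
- Section 9.7.6.1 says that patients "can only contribute to one exposure category at any given point of time", and section 9.9 repeats that at a given time "patients will contribute time at risk to a single exposure category, either rivaroxaban or SOC".
- In the exposure sensitivity analysis of 9.7.6.1, "only the first treatment agent episode will be considered", with a 30-day carry-over added.

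No section says which rule prevails when a short rivaroxaban course lies between two SOC episodes.

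**The concern.** The merge rule sensibly joins neighbouring SOC agents, such as heparin followed by a VKA. As worded, it also joins two SOC episodes that are apart only because the child was on rivaroxaban. The merged episode then covers days on which the child was, by the protocol's other rules, a rivaroxaban patient.

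Sections 9.3.1 and 9.7.4 draw person-time and events for the co-primary bleeding outcomes from these episodes. If the merged SOC episode takes precedence, the rivaroxaban days and any bleed on them move to SOC. An SOC flank before rivaroxaban is the expected pattern: section 9.2.3.1 says that in theory every rivaroxaban patient is a switcher. An early return to SOC is then enough to trigger the rule. Section 9.6 says that data are generally analysed locally, so programmers in different countries could also resolve the conflict differently.

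**Working it through.** The plan attaches no figure to this rule, so there is none to reproduce. The check applies the rules to one assumed history.

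**Inputs.** From section 9.3.1: SOC episodes are merged if the gap is under 30 days. From the Figure 1 notes: an episode ends at a switch. From 9.1, 9.2.2.1, 9.7.6.1 and 9.9: time is credited to each category in turn, one at a time. Assumed for illustration: SOC for 10 days, rivaroxaban for d days, SOC for 60 days, with no days between them. The first SOC episode ends on the day of the rivaroxaban record, and no carry-over is added because a switch is observed.

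**Formulas.**

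- Gap between the two SOC episodes = d.
- As-treated: SOC = 10 + 60 = 70 days; rivaroxaban = d days.
- Literal merge, for d < 30: one SOC episode of 10 + d + 60 = 70 + d days. If it takes precedence, rivaroxaban = 0 days.
- For d of 30 or more the merge rule does not apply.

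| d (days) | As-treated: SOC / rivaroxaban | Merge applies? | Literal merge, SOC taking precedence: SOC / rivaroxaban |
|---|---|---|---|
| 10 | 70 / 10 | yes | 80 / 0 |
| 20 | 70 / 20 | yes | 90 / 0 |
| 29 | 70 / 29 | yes | 99 / 0 |
| 30 | 70 / 30 | no | 70 / 30 |
| 31 | 70 / 31 | no | 70 / 31 |
| 45 | 70 / 45 | no | 70 / 45 |

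**Does the end-at-switch rule prevent this?** Not by itself. It closes the first SOC episode at the rivaroxaban record. The merge rule works on episodes that have already been built and closed. The switch therefore creates the very gap that the merge rule bridges when SOC resumes within 30 days.

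**Same-agent grace rule.** For heparin, rivaroxaban, heparin, the wording in 9.3.1 closes the heparin episode only after a gap of more than 30 days between heparin prescriptions. It does not mention an intervening rivaroxaban record either. Here the Figure 1 notes help more directly, since they list a switch as a separate way for an episode to end. But the two heparin episodes that result are again open to merging.

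**Would the sensitivity analysis show it?** In an SOC, rivaroxaban, SOC sequence, the analysis in 9.7.6.1 keeps the first SOC agent's episode and drops the rivaroxaban episode. Its 30-day carry-over then runs over the same days: with d = 20, all 20 rivaroxaban days fall inside it. It cannot test how those days should be classified.

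**The case against.** The strongest reply is that the rest of the protocol already settles the matter. A rivaroxaban record is a switch, a switch ends the SOC episode, and repeated switching with time credited to each category is expressly allowed. The merge sentence speaks of individual SOC agents, and section 9.3.1 explains that these are pooled into one group, so its natural purpose is to join adjacent SOC agents. Precedence between episode-building rules could also be left to the SAP, to which section 9.7.1 assigns exposure definitions.

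Much of this stands. Joining adjacent SOC agents is probably the intent, and absorption into SOC is only one reading of conflicting rules. It does not remove the point: the text lacks the limit that the intent needs, and the end-at-switch rule does not supply it. Because the protocol fixes the merge rule itself, a SAP that follows it inherits the conflict.

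A reader might infer two stronger consequences that the documents do not support:

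- **Double counting.** Keeping both the merged SOC episode and the rivaroxaban episode would give 90 + 20 = 110 person-days over 90 calendar days. Sections 9.7.6.1 and 9.9 rule this out for the main analysis.
- **Understated switching.** Episodes are built by agent, switches are defined between agents, and sections 9.3.2.1.2 and 9.7.3 describe the sequence of agents or classes. Forming the SOC category need not erase those records.

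The setting also limits the reach. Section 9.9 says that SNDS, the source in which bleeding is expected to be reportable, does not capture inpatient drugs. A child switched in hospital appears there as a rivaroxaban initiator, with no earlier SOC episode to merge. The pattern in SNDS needs outpatient SOC on both sides of the rivaroxaban course.

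**Conclusion.** The point holds as a conflict between stated rules. Used literally, the merge rule in 9.3.1 places one SOC episode over any rivaroxaban course shorter than 30 days that lies between SOC episodes. This contradicts the end-at-switch, multiple-switch and one-category-at-a-time rules. If the SOC episode takes precedence, all rivaroxaban time in such a course moves to SOC, with any bleed in it. Courses of 30 days or more are not affected, given the assumption that SOC stops at the switch and resumes when rivaroxaban ends.

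The effect on the bleeding results cannot be derived, because the documents do not say how often the pattern occurs. A reader might infer a bias in favour of rivaroxaban, on the view that short courses are those stopped for bleeding. The documents do not show this: bleed-free short courses would move too and take person-time with them, so the net effect on either rate is unknown. A reader might also infer that the SNDS bleed count would fall below the French reporting limit of ten. The expected count is 219 × 5.6% = 12.3, but nothing in the protocol says how many of those bleeds fall in affected courses. Its own range of 5 to 20 already spans the limit.

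The correction should be made before programming begins. It is not a reason to doubt the design.

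**What to change.** Add to section 9.3.1 that SOC episodes are merged, and the same-agent grace period is applied, only when no rivaroxaban prescription is recorded between them. State that a rivaroxaban record ends the current SOC episode on that date, and that a later SOC record starts a new SOC episode and counts as a switch back. Carry the same wording into the SAP and the common programming specification, so that all data sources apply it alike.

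The cost is one or two sentences and the matching programming rule. No additional data are needed, and the change only brings 9.3.1 into line with 9.1, 9.2.2.1, 9.7.6.1 and 9.9.

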9.3.2. Outcomes

9.3.2.1. Primary outcomes

9.3.2.1.1. Patient characteristics

The following patient characteristics, including risk factors for VTE will be considered:

- Demographic characteristics of patients: age, sex; bodyweight at index date and gestational age, if available
- Characteristics of index VTE, if available (depending on the granularity of codes):
 - Type of location of VTE
 - Central venous catheter related thrombosis
 - Symptomatic versus asymptomatic VTE
- Co-morbidities reported in the previous six months before index date, or since date of birth for children less than six months:
 - Major organ disease (cardiac, gastrointestinal, renal, neurological)
 - Malignancy (active cancer, haematological cancer, solid tumour)
 - Thrombophilia (congenital or acquired), including antithrombin, protein C or Protein S deficiency, factor V Leiden or prothrombin mutation
 - Major surgery or trauma
 - Major infectious disease
 - Major congenital venous anomaly
 - Use of central venous catheter
 - Morbid obesity
 - Hypertension
- Prior treatments reported in the previous six months before index date (or since date of birth for children less than six months): all drugs by third or fourth ATC level
- Comedication during follow-up: all drugs by third or fourth ATC level, and subgroup of all drugs that can increase the risk of bleeding, such as non-steroidal anti-inflammatory drugs, antiplatelets and aspirin
- Health resource utilization in the previous six months before index date (or since date of birth for children less than six months), e.g., marker of health status of the patients, including

- Outpatient visits
- Hospital admissions
- Length of hospital stay
- Admission to intensive care unit
- Duration of oral, nasogastric/gastric feeding before index date (identified via procedure codes), if available

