9.2.3. Selection criteria

9.2.3.1. Inclusion criteria

Participants are eligible to be included in the study only if all of the following criteria apply:

- Evidence of initiation of an anticoagulant therapy (index drug), either rivaroxaban oral suspension or other anticoagulation therapies (heparins, VKAs, other DOACs). Initiation will be defined as a first record of any anticoagulation therapy (rivaroxaban or SOC) without any anticoagulation therapy in the previous 6 months, or since date of birth for children less than 6 months (see codes for anticoagulant drugs in [Annex 3](#)).
- Evidence of a prior VTE diagnosis (index VTE), defined as the presence of at least one primary/main or secondary diagnosis code for VTE recorded in inpatient setting in the previous 30 days (see preliminary list for VTE codes in [Annex 3](#)).
- Age less than two years on index date.
- Baseline period for availability of patient data history in the data source. A minimal baseline period of six months before index date for children aged between six months and two years, and a baseline period since birth for children less than six months of age will be required.

According to its indication, rivaroxaban oral suspension should be used after at least five days of initial parenteral anticoagulation treatment. In order to describe the actual clinical practice in real world settings, there will no requirement on this initial parenteral anticoagulation treatment to include patients in the study population, so patients will be identified independently of this. In theory, all patients receiving rivaroxaban should be switchers. In practice, they may appear as initiating directly with rivaroxaban: the observed initial anticoagulant therapy might be different from the actually received initial therapy, if patients have switched drug during hospital stay and if inpatient drug data is not captured. Depending on availability of inpatient drug data in each data source, the observed initiation of the anticoagulant therapy will be identified either in outpatient or in inpatient setting, as shown in [Figure 2](#) below (see [Section 9.4](#)).

SOC for treatment of VTE in children usually include UFH, LMWH and VKA and may vary across countries. With other DOACs receiving indication for VTE in paediatrics, SOC may also evolve over time.

Figure 2 Visualization of patient journey

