9.4.2. Details of data sources

In order to meet the study objectives, the following data sources will be considered:

France – SNDS

The French National Health Data System (SNDS) is the largest and most comprehensive healthcare dataset available in Europe with a 10-year longitudinal follow-up for more than 50 million patients. SNDS includes anonymized administrative and healthcare claims data from the French national health care insurance system databases. In particular data from SNIIRAM (Système national d'information interrégimes de l'Assurance maladie) which consist of: hospital discharge summaries (Programme de Médicalisation des Systèmes d'Information, [PMSI]), all outpatients reimbursed health expenditures (données de consommation inter-régimes, [DCIR]), and national death registry (CépiDC database on causes of death) (9). SNDS data consist of anonymized data of reimbursed claims for all patients affiliated with compulsory health insurance providers (the general scheme covers about 86% of France residents, and 14 other schemes cover the rest) and cover about 99% of French residents.

Data from DCIR and PMSI have been linked for each patient to allow for follow-up across different settings of care including outpatient practice and hospital admissions related to medicine, surgery and obstetrics. At this time, date of death from the national death registry is linked to the other data for all the periods. Causes of death are progressively integrated (only available for 2013, 2014, and 2015). Healthcare use of the patient can then be tracked since birth/first residence in France for 10 years even if a subject is not working, changes occupation or retires and irrespective of socio-economic status. There is no loss to follow-up except for emigration.

For more information see [Annex 3](#).

Denmark – National Registers

The Danish data sources for this study are owned, run and made accessible to research projects by Danish governmental and regional authorities (10). The Danish health care system is a tax-funded, one-payer system with full coverage for all residents (5.8 million) and some co-payment from the patients for prescriptions drugs and dental work.

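### Permanent conditions count only if reported in the six months before index, so they may be under-recorded in children aged 6 to under 24 months, the older of the two planned age subgroups

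*Protocol*

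**What the plan says.** Section 9.3.2.1.1 lists the patient characteristics, which are primary outcomes. The co-morbidity block opens with a single window for all its items: "Co-morbidities reported in the previous six months before index date, or since date of birth for children less than six months". Under it stand time-limited items (major surgery or trauma, major infection, central venous catheter use) beside items that do not go away: "Thrombophilia (congenital or acquired), including antithrombin, protein C or Protein S deficiency, factor V Leiden or prothrombin mutation" and "Major congenital venous anomaly". Cardiac and other major organ disease, much of it chronic, is there too. No item has an ever-recorded rule.

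Section 9.2.3.1 sets the history needed for entry: "A minimal baseline period of six months before index date for children aged between six months and two years", and history since birth for younger infants. This is a floor, not a limit on the data. The upper age bound is "Age less than two years on index date".

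On earlier records, section 9.4.2 says of the French source: "Healthcare use of the patient can then be tracked since birth/first residence in France for 10 years". For Denmark and Sweden it describes a personal identifier, given at birth or on immigration, that supports follow-up from then on. It makes no such statement for SIDIAP.

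Section 9.7.7 plans a subgroup analysis of primary and secondary outcomes by age at index, split at six months. The limitations in section 9.9 do not mention the look-back.

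**The concern.** A short window suits a factor whose recency matters, such as a recent operation or a catheter in place. It suits a permanent condition poorly, because the question there is whether the child has it, not whether someone coded it lately.

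Take a child with antithrombin deficiency coded at 3 months. Indexed at 5 months, the child is recorded as having thrombophilia. Indexed at 20 months, with no repeat code between months 14 and 20, the same child is recorded as not having it, although the earlier code may be in the source.

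At stake is the first primary objective, the description of clinical characteristics. Section 7.2 names congenital heart disease and thrombophilia among the VTE risk factors, so these are core rows of the table. Because truncation begins at the age of the subgroup split, a lower recorded frequency in the older group could reflect the definition and not the children.

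**Working it through.** The protocol states no figure that depends on this definition, so there is nothing to reproduce. The check has three parts.

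**1. How much history the window leaves out.** Inputs: a six-month window (9.3.2.1.1) and age at index below 24 months (9.2.3.1). For a child of age *a* months observed since birth, the share of life inside the window is min(1, 6/*a*), and the history ignored is max(0, *a* − 6) months.

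| Age at index (months) | Share of life in window | Months ignored |
|---|---|---|
| under 6 | 100% | 0 |
| 9 | 6/9 = 67% | 3 |
| 12 | 6/12 = 50% | 6 |
| 18 | 6/18 = 33% | 12 |
| just under 24 | 6/24 = 25% | 18 |

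If age at index were uniform over 6 to 24 months (assumption), the mean share would be (6/18) × ln(24/6) = 0.333 × 1.386 = 0.46. These are shares of time, not shares of codes lost.

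**2. What that could do to a recorded frequency.** Let *p* be the frequency of a permanent condition with any code by index date, and *c* the proportion of those children with at least one code inside the window. At 6 to under 24 months the recorded frequency is *p* × *c*. Below six months *c* = 1 by construction, so it is *p*. Both *p* and *c* are assumptions; the protocol gives neither.

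| *c* | *p* = 10%, older group | *p* = 30%, older group |
|---|---|---|
| 0.5 | 5% | 15% |
| 0.7 | 7% | 21% |
| 0.9 | 9% | 27% |
| 1.0 | 10% | 30% |

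The younger group would show 10% or 30% throughout. The whole effect turns on *c*.

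**3. What the protocol implies about *c*.** Section 9.2.3.1 requires an inpatient VTE diagnosis within the 30 days before index. Every included child therefore has a coded hospital contact that normally falls inside the window, and a known lifelong condition may be coded again there. The co-morbidity definition is not restricted to inpatient codes. Table 3 lists specialist outpatient diagnoses for Denmark and Sweden, and primary care linked to hospital admissions for SIDIAP. Annex 3 describes long-term disease status in the French source, though registration is not mandatory. All this pushes *c* upwards, but nothing in the protocol fixes it at 1.

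With all available history used for permanent conditions, the window would cover 100% of life in both age groups for children observed since birth.

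**The case against.** Five arguments can be made for the present rule.

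- **The index admission re-codes the condition.** This has force. It means the size may be small and that no firm number can be given. A reader might model re-coding as random at some assumed yearly rate and read off the proportion of children with no code in six months. That would describe children with no guaranteed admission, whereas this cohort is selected for a recent one, so such figures do not apply.
- **Infants are under-recorded too.** A one-month-old has only one month in which to be diagnosed or tested. This stands: infants are free of look-back truncation, not of under-recording. In absolute months the older children already have the longest window, and lengthening it widens the gap in observation time. That is a real trade-off, but it does not justify setting aside a known permanent diagnosis.
- **Earlier data may not exist.** For France and the Nordic countries they run from birth, or from first residence or immigration. For SIDIAP the protocol does not say. The fix should therefore refer to available history.
- **The statistical analysis plan will settle it.** Sections 9.3.2.1.2 and 9.7.1 defer operational definitions, but section 9.3.2.1.1 already fixes the window, and a plan that follows the protocol inherits it.
- **The study is descriptive.** This is so, and it limits the reach. A reader might infer that bleeding or recurrent-VTE results are biased. They are not affected: section 9.7.4 plans crude estimates, and the ENCePP checklist marks confounding control as not applicable. A reader might also infer false calendar trends or false rivaroxaban/SOC differences. Section 9.3.2.2.1 gives no window for medical history, and a constant rule distorts such tables only if age mix or re-coding differs between the groups compared.

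**Conclusion.** The point holds as a risk of under-recording, not as a demonstrated loss. As section 9.3.2.1.1 stands, a permanent condition coded early and not re-coded in the six months before index is recorded as absent, and this can happen only at six months of age or older. Truncation begins at the subgroup split, so differences between the two age groups in these rows may be partly artefact. For a child observed since birth, the history set aside grows from nothing at six months to about 18 months just under two years. The resulting fall in recorded frequency depends on how often conditions are re-coded; it cannot be derived from the protocol and may be small. The effect is confined to the permanent and chronic rows of the patient-characteristics tables. These serve a primary objective and the correction is cheap, so the change is worth making.

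**What to change.** In section 9.3.2.1.1, split the co-morbidity list by type:

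- Define clearly permanent or chronic conditions (congenital thrombophilia, major congenital venous anomaly, congenital cardiac and other chronic organ disease) by any record from birth, or from first available data, to index date, at every age.
- Keep the six-month window for time-limited factors: surgery, trauma, infection and catheter use.
- Report the available look-back length by age group, and flag children not observed since birth.

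The cost is a sentence or two in the protocol and the matching variable definitions. No new data source is needed where earlier records are held; for SIDIAP the available history should be confirmed. The downside is that look-back length then varies with age and with date of entry to the source, which is why it should be reported beside these rows.
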